#### 9.2.2.2 Computer Systems

Data will be processed using a validated computer system conforming to regulatory requirements.

#### 9.2.2.3 Data Entry

Data must be recorded in to the EDC system in a timely manner as the study is in progress. All site personnel must log into the system using their secure user name and password in order to enter, review, or correct study data. These procedures must comply with the appropriate international regulations. All passwords will be strictly confidential.

#### 9.2.2.4 Medical Information Coding

For medical information, the following thesauri will be used:

- Latest version of MedDRA for AEs and medical history, and
- WHO Drug Dictionary for prior and concomitant medications.

#### 9.2.2.5 Data Validation

Validation checks programmed within the EDC system, as well as supplemental validation performed via review of the downloaded data will be applied to the data in order to ensure accurate, consistent, and reliable data. Data identified as erroneous, or data that are missing, will be referred to the investigative site for reconciliation/resolution through data queries.

The eCRFs must be reviewed and approved/signed by the PI.

#### 9.2.3 Source Documents

Source documents provide evidence for the existence of the subject and substantiate the integrity of the data collected. Source documents are filed at the PI's site. Data reported on the eCRFs must be consistent with the source documents or the discrepancies must be explained. The PI or designee may need to request previous medical records or transfer records from another institution, depending on the study; also, current medical records – not just shadow charts – must be available.

CONFIDENTIAL
PAGE 65 OF 80

The following data to be reported on the eCRF should be included and derived from source documents:

- Subject identification (subject number, gender, date of birth/age)
- Subject participation in the study (subject number, date informed consent given)
- Dates of subject's visits
- Medical history
- Medication history
- AEs (onset and end)
- SAEs (onset and end)
- Originals or copies of laboratory results: All laboratory reports must be reviewed by the PI and/or his/her designee; any abnormal findings should be addressed.
- Conclusion of subject's participation in the trial.

#### 9.2.4 Direct Access to Source Data/Documents

The PI/institution will permit study-related monitoring, audits, IEC/IRB reviews and regulatory inspections by providing direct access to all related source data/documents. Case report forms and all source documents, including progress notes and copies of laboratory and medical test results, must be available at all times for review by the Sponsor's clinical trial monitor(s), auditor(s) and inspection by applicable regulatory authorities. The on-site monitor will review all eCRFs and ICFs. The accuracy of the data will be verified by reviewing the documents described in Section 9.2.3.

All ECG's will be conducted locally. A photocopy should be made of the ECG, and assessment of clinical significance should be conducted by site staff personnel delegated to do so.

#### 9.2.5 Trial Monitoring

It is the responsibility of the Principal Investigator to ensure that the study is conducted in accordance with the protocol, with ICH GCP, and with all other applicable regulatory requirements and that valid data are entered into the eCRFs.

To achieve this objective, the study monitor's duties are to aid the PI, and at the same time, the Sponsor in the maintenance of complete, legible, well-organized and easily retrievable data. Before the enrolment of any subject in this study, the Sponsor or their designee will review with the PI and site personnel the following documents: protocol, Investigator's

Approved by: Protocol No.: SARO.17.010
[name] [name] Version No.: 7.0

CONFIDENTIAL

**PAGE 66 OF 80** 

Brochure, eCRFs and procedures for their completion, informed consent process, and the procedure for reporting SAEs.

The PI will permit the Sponsor or their designee to monitor the study as frequently as deemed necessary to determine that data recording and protocol adherence are satisfactory. During the monitoring visits, information recorded on the eCRFs will be verified against source documents and requests for clarification or correction may be made. After the eCRF data is entered by the site, the monitor will review the data for safety information, completeness, accuracy, and logical consistency. Computer programs that identify data inconsistencies may be used to help monitor the clinical study. If necessary, requests for clarification or correction will be sent to PIs. The PI and his/her staff will be expected to cooperate with the monitor and provide any missing information.

All monitoring activities will be reported and archived. In addition, monitoring visits will be documented at the investigational site by signature and date on the study-specific monitoring log.

#### 9.3 QUALITY ASSURANCE AUDIT

A quality assurance audit of this study may be conducted by the Sponsor or Sponsor's designees. The quality assurance auditor must have access to all medical records, the study-related files and correspondence, and the informed consent documentation that is relevant to this clinical trial.

#### 9.4 PROCEDURES

#### 9.4.1 Adverse Events

All AEs occurring during the course of the clinical trial from the signing of the informed consent onwards will be collected, documented, and reported to the Sponsor by the PI or designee according to the specific definitions and instructions detailed in this section.

An AE is defined as any untoward medical occurrence in a clinical investigation subject administered a pharmaceutical product and which does not necessarily have a causal relationship with this treatment.

Any medical condition already present at screening should not be reported as an AE unless the medical condition or signs or symptoms present at baseline changes in severity or seriousness at any time during the study. In this case, it should be reported as an AE.

PAGE 67 OF 80

Clinically significant abnormal laboratory or other examination (e.g. electrocardiogram) findings that are detected during the study or are present at screening and significantly worsen during the study should be reported as AEs. The PI will exercise his or her medical and scientific judgment in deciding whether an abnormal laboratory finding or other abnormal assessment is clinically significant. Clinically significant abnormal laboratory values occurring during the clinical study will be followed until repeat tests return to normal, stabilize, or are no longer clinically significant. Any abnormal test that is determined to be an error does not require reporting as an AE.

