#### 9.4.5 Expected Adverse Events

Adverse events reported by 2% or more patients treated with Saroglitazar magnesium during the double-blind, active-controlled study with pioglitazone as the comparator regardless of causality included gastritis and asthenia. In the double-blind placebo controlled study, AEs reported by 2% or more patients treated with Saroglitazar magnesium included gastritis, dyspepsia, pyrexia and pain. The details of AE(s) experienced during the Saroglitazar magnesium studies are mentioned in the IB. Principal Investigator(s) are advised to provide protocol education for patients and caregivers for potential symptoms of adverse effects that should be reported to the site/PI, such as skeletal muscle pain, weight gain, peripheral edema, shortness of breath, hypoglycaemia, etc.

CONFIDENTIAL
PAGE 71 OF 80

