### 8.3.2 Adverse Events

The applicable definition of an Adverse Event (AE) is in the study protocol section 9.4. A treatment-emergent AE (TEAE) is an event not present prior to exposure to study drug or any pre-existing event that worsens following exposure to study drug. The period for treatment-emergent AE analysis starts from the first exposure to the study drug until the patient exits the study.

Descriptive summaries (frequencies and percentages) for specific TEAEs will be presented by system organ class and preferred term according to the Medical Dictionary for Regulatory Activities (MedDRA Version 21.0) dictionary. In addition to an overall presentation of all TEAEs, reports will be generated for special classes of TEAEs such as drug related TEAEs, serious TEAEs, Maximum severity and TEAEs resulting in treatment discontinuation. These reports will be supported by individual patient listings, as necessary.

Adverse events will be counted by the number of events as well as the number of patients. For the summaries which count the number of patients, multiple TEAEs with the same MedDRA preferred term within the same patient will only be counted once.

Only patient listings will be provided for AEs that occur after signing informed consent but prior to exposure to study drug. These listings will comprise all events occurring during this period in any patient who consented to participate in the study.

These listings will at least contain but not limited to information such as onset and resolution times, maximum severity, causal relationship to study drug and action taken.

Statistical Analysis Plan			
Version Number:	1.0	Date:	31 Dec 2021
Protocol Number:	SARO.17.010	Sponsor Name:	Zydus Therapeutics Inc.

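### The AE rule for conditions present at screening omits increased frequency, so the primary safety summary may under-count symptoms that worsen on drug

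*Protocol*

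**What the plan says.** Protocol 9.4.1 sets a default for conditions that patients bring into the study: "Any medical condition already present at screening should not be reported as an AE". There is one exception: "unless the medical condition or signs or symptoms present at baseline changes in severity or seriousness at any time during the study". When it applies, "In this case, it should be reported as an AE".

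Two other sentences in 9.4.1 bear on this. The general definition reads "An AE is defined as any untoward medical occurrence in a clinical investigation subject administered a pharmaceutical product". For clinically significant laboratory and examination findings the test has a direction: those that "are present at screening and significantly worsen during the study should be reported as AEs".

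SAP 8.3.2 takes its AE definition from protocol section 9.4. It treats as treatment-emergent any new event, or "any pre-existing event that worsens following exposure to study drug". It does not say what counts as worsening. It tabulates both numbers of events and numbers of patients.

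Safety is the primary endpoint (protocol 6.1.1), and protocol 8.2.2 summarises AEs by counts and percentages. Protocol 9.4.5 asks investigators to teach patients to report symptoms "such as skeletal muscle pain, weight gain, peripheral edema, shortness of breath, hypoglycaemia, etc".

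**The concern.** Several of the complaints named in 9.4.5 come and go. For such a complaint, a drug effect can appear as more episodes of the same grade. That is a change in neither severity nor seriousness, so a site following 9.4.1 literally would not open an AE record.

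The collection rule then decides what the analysis can see. The SAP may supersede the protocol on analysis (SAP section 1), but it cannot recover an event that was never entered. Any loss would run towards making the drug look safer. With one arm and 15 patients, no control group would reveal it. Protocol 5.9 also lets the investigator halt the study on an adverse trend, and AE incidence is among the things evaluated there.

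**Working it through.** The plan states no figure on this point, so the check is a comparison of the two rules, case by case, for a condition present at screening.

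| Course on study drug | Protocol 9.4.1: report? | SAP 8.3.2: treatment-emergent? |
|---|---|---|
| Unchanged | No | No |
| Mild becomes moderate | Yes, severity changed | Yes |
| Mild stays mild, not serious, but more frequent | No, neither listed attribute changed | Yes if worsening has its ordinary meaning, but there is no record to count |
| Moderate becomes mild | Fits the undirected verb, but is not an untoward occurrence | No, it has not worsened |
| Clinically significant laboratory or examination finding that significantly worsens | Yes, under its own sentence | Yes |

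Only the third row loses information that the analysis might want.

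**Which complaints fall in the third row.** The other routes of capture are:

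- Hypoglycaemic episodes: all go into the eCRF (protocol 5.8.1), although that section does not say as AEs.
- Weight: recorded at every physical examination (6.1.2.2).
- Oedema and breathlessness: the examination covers heart, lungs and extremities (6.1.2.2). Results are listed for all enrolled patients (SAP 8.3.4), and examination findings have the directional rule in 9.4.1.
- Muscle: creatine phosphokinase is a safety laboratory test (Table 3), and 6.2.10 lets the investigator call any abnormal test result an AE.

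These routes rest on a test, a measurement or a visible sign, except the hypoglycaemia record. A symptom known only from the patient's account, with muscle pain the clearest example, is not covered by them.

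**Scale.** Inputs: 15 patients planned (protocol 4.1), all assumed to be dosed and so in the safety population.

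- Loss per affected patient = 1/15 = 6.7 percentage points in the row for that preferred term, if the patient has no other record under the term.
- The documents give no count of affected patients. Assuming 1 to 3, the loss in a row they all share is 1/15 = 6.7 to 3/15 = 20.0 points.
- The row for any treatment-emergent AE falls only for an affected patient who has no other such event.

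**The case against.** The case on the other side has real content.

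- **More frequent often means more severe.** For events outside CTCAE, protocol 9.4.4 grades severity by disruption of daily activity and need for treatment. Episodes frequent enough to disrupt activity would move up a grade and be reported. This stands, but the scale does not name frequency and nothing requires a regrade.
- **Entry criteria thin out the affected group.** Protocol 4.3 excludes chronic uncontrolled pain, myopathy or active muscle disease, abnormal creatine kinase, unstable angina, NYHA III-IV or worsening heart failure, and recent weight change above 5%. This also stands. Mild muscle pain, oedema or breathlessness is not excluded in itself.
- **The SAP does not define worsening.** So it cannot be shown that its authors meant to count a rise in frequency alone. That is fair, and it is a reason to define the term.
- **Numerical stopping triggers are little affected.** Protocol 5.9, 5.9.2 and 7.5 use related SAEs or Grade 3 and above events. Low-grade episodes would not move them. Only the judgement of an adverse trend in 5.9 could be touched.

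A reader might also infer that such a change is never recorded anywhere. The routes of capture above contradict that.

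A reader might further infer that improvements, which literally satisfy the verb in 9.4.1, would inflate the primary result. They would not: an improvement is not untoward under the definition in the same section, and SAP 8.3.2 counts a pre-existing event only if it worsens. The missing direction is a drafting flaw that at most produces stray records.

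**Conclusion.** The point holds as a gap in AE capture. Under 9.4.1 as written, a pre-existing symptom that becomes more frequent at an unchanged grade and seriousness is not to be reported as an AE, and SAP 8.3.2 cannot put it back. The primary safety summary may be under-counted by 6.7 percentage points per affected patient in a given preferred-term row.

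This is a possible under-count, not a demonstrated bias. The number of affected patients is unknown, and the range of 1 to 3 is an assumption used only to show scale. The conclusion assumes that sites follow the wording literally and that worsening in the SAP carries its ordinary meaning. The exposure is confined mainly to purely symptomatic complaints. The point has modest weight, but it deserves correction because the rule feeds the primary endpoint and the repair is small.

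**What to change.** In protocol 9.4.1, replace the test for pre-existing conditions with *worsens in severity, frequency or seriousness*. This supplies both the missing attribute and the missing direction, and brings the sentence into line with the rule for laboratory and examination findings in the same section. In SAP 8.3.2, define worsening of a pre-existing event in the same words.

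The cost is a few more AE records and one protocol amendment. Under protocol 9.5 the amendment must be signed by all signatories and submitted to the regulatory authorities and the IEC/IRB. It affects only data collected after it takes effect. For patients already followed under version 7.0 (the SAP is dated 31 December 2021), the clinical study report should state the limitation.

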#### 9.4.2 Serious Adverse Events

A serious adverse event is any AE occurring at any dose or during any use of Sponsor's product that:

- Results in death;
- Is life threatening;
- Results in persistent or significant disability/incapacity;
- Results in inpatient hospitalization or prolongs an existing inpatient hospitalization;
- Is a congenital anomaly/birth defect;
- Is another important medical event that may not result in death, be lifethreatening, or require hospitalization may be considered serious when, based upon appropriate medical judgment, they may jeopardize the patient or subject and may require medical or surgical intervention to prevent one of the outcomes listed above.

#### Serious Adverse Event Reporting-Procedures for Investigator:

#### **Initial Reports:**

Any SAE, or follow-up to a SAE, including death due to any cause that occurs to any subject from the time the consent is signed through 4-week following cessation of treatment, whether or not related to the Sponsor's product, must be reported to the Sponsor within 24 hours of the knowledge of the occurrence to investigational site.

Additionally, any SAE, considered by the PI or designee, who is a qualified physician, to be related to the Sponsor's product, that is brought to the attention of the PI or designee at any

[figure not shown]

CONFIDENTIAL PAGE 68 OF 80

time outside of the time-period specified in the previous paragraph also must be reported immediately to the Sponsor.

To report an SAE, complete the SAE form electronically in the electronic data capture (EDC) system for the study. Once the form is completed, the CRO/Sponsor Safety personnel will be notified electronically. If the event meets serious criteria, and, it is not possible to access the EDC system, send an email to CRO/Sponsor or call the CRO/Sponsor SAE hotline (phone number listed below), and email the completed SAE form/information to CRO/Sponsor (email listed below) within 24 hours of awareness. When the EDC system becomes available, the SAE information must be entered within 24 hours of the system becoming available.

Safety Contact Information:

#### Follow-Up Reports

All patients with SAEs must be followed-up for outcome. Within 24 hours of receipt of follow-up information, the PI or designee must update the SAE form electronically in the EDC system and submit any supporting documentation (e.g., subject discharge summary or autopsy reports) to Sponsor Clinical Safety via fax or e-mail. If it is not possible to access the EDC system, refer to the procedures outlined above for initial reporting of SAEs.

CONFIDENTIAL
PAGE 69 OF 80

#### 9.4.3 Follow-up of Adverse Events

All AEs experienced by a patient, irrespective of the suspected causality, will be monitored until the AE has been resolved, any abnormal laboratory values have returned to baseline or stabilized at a level acceptable to the PI and Medical Expert(s), until there is a satisfactory explanation for the changes observed, until the patient is lost to follow-up, or until the patient has died.

### 9.4.4 Evaluating Adverse Events

Each AE will be assessed by the PI or a medically-qualified investigator with regard to the following categories:

### **Severity**

The PI or designee will provide an assessment of the severity of each AE by recording a severity rating on the appropriate AE reporting page of the patient's eCRF. The Common Terminology Criteria for Adverse Event (CTCAE) (Version 4.03 or higher) system will be used for reporting and grading AEs severity of events not classified in CTCAE will be assessed according to the following scale:

- Mild: Event is usually transient and easily tolerated, requiring no special treatment and causing no disruption of the patient's normal daily activities.
- Moderate: Event introduces a low level of inconvenience or concern to the patient
  and may interfere with daily activities, but is usually improved by simple therapeutic
  measures. Moderate experiences may cause some interference with functioning.
- Severe: Event interrupts the patient's normal daily activities and generally requires systemic drug therapy or other treatment. Severe events are usually incapacitating.

#### **Causality**

For all AEs, the PI or designee will provide an assessment of causal relationship to study drug. The causality assessment must be recorded on the appropriate AE reporting page of the patient's eCRF.

Causal relationship will be classified according to the following criteria:

Unrelated

PAGE 70 OF 80

- Possibly related: Suggests that the association of the AE with the study drug is unknown. However, the AE is not reasonably supported/explained by other conditions.
- Probably related: Suggests that a reasonable temporal sequence of the AE with study drug administration exists and, based upon the PI's clinical experience, the association of the AE with study drug seems likely.
- Definitely related: Suggests that a causal relationship exists between the study drug and the AE, and other conditions (concomitant illness, progression or expression of the disease state, reaction to concomitant medication) do not appear to explain the AE.
- Unknown

#### **Outcome**

Outcome of AEs will be defined according to the International Council for Harmonisation (ICH) Topic E2B, ICH Guideline, as follows:

- Recovered/Resolved
- Recovered/Resolved with sequelae
- Recovering/Resolving
- Not Recovered/Not Resolved
- Fatal/results in death
- Unknown

#### 9.4.5 Expected Adverse Events

Adverse events reported by 2% or more patients treated with Saroglitazar magnesium during the double-blind, active-controlled study with pioglitazone as the comparator regardless of causality included gastritis and asthenia. In the double-blind placebo controlled study, AEs reported by 2% or more patients treated with Saroglitazar magnesium included gastritis, dyspepsia, pyrexia and pain. The details of AE(s) experienced during the Saroglitazar magnesium studies are mentioned in the IB. Principal Investigator(s) are advised to provide protocol education for patients and caregivers for potential symptoms of adverse effects that should be reported to the site/PI, such as skeletal muscle pain, weight gain, peripheral edema, shortness of breath, hypoglycaemia, etc.

CONFIDENTIAL
PAGE 71 OF 80

#### 9.4.6 Pregnancy

At the Screening Visit and the End of treatment Visit every female subject of childbearing potential will be tested for serum pregnancy test and urine pregnancy test will be performed at other visits. Women are advised not to become pregnant during the study and for at least 4-week after the end of the treatment period. Adequate contraceptive measures shall be used to prevent pregnancy. Even when contraceptive methods are used, there is a small risk that pregnancy might occur. In case a patient becomes pregnant, then she will be withdrawn from the study and adequate monitoring of the patients will be conducted.

Although pregnancy and lactation are not considered AEs, it is the responsibility of the PI or their designees to report any pregnancy or lactation in a patient (spontaneously reported to them) that occurs during the study. All patients who become pregnant must be followed to the completion/termination of the pregnancy. Pregnancy outcomes of spontaneous abortion, missed abortion, benign hydatidiform mole, blighted ovum, fetal death, intrauterine death, miscarriage and stillbirth must be reported as serious events (Important Medical Events). If the pregnancy continues to term, the outcome (health of infant) must also be reported.

The PI or designee should report the pregnancy to the Sponsor within 24 hours of being notified. The Sponsor will then forward the completed Exposure-in-Utero form to the PI.

